### 7.1.1 Use of Electronic Diaries

At the time of consent, participants' parent(s)/LAR(s) must confirm they will be willing to complete an eDiary using either an application downloaded to their smartphone or using a device that is provided at the time of enrollment. Before enrollment on Day 1, participants' parent(s)/LAR(s) will be instructed to download the eDiary application or will be provided an eDiary device to record solicited ARs ([Section 7.4.3](#)) on Day 1. Based on availability, smartphone devices may be provided to those participants' parent(s)/LAR(s) who do not have their own device to use for eDiary activities.

At each injection visit, participants' parent(s)/LAR(s) will be instructed (Day 1) or reminded (Day 29, BD-Day 1, if applicable) on thermometer (oral/tympanic) usage to measure body temperature, ruler usage to measure injection site erythema and swelling/induration (hardness), and assessment for localized axillary swelling or tenderness on the same side as the injection arm/thigh.

At each injection visit, participants' parent(s)/LAR(s) will record data into the eDiary starting approximately 30 minutes after injection under the supervision of the study site staff to ensure successful entry of assessments. The study site staff will perform any retraining as necessary. Participants' parent(s)/LAR(s) will continue to record data in the eDiary after they leave the study site, preferably in the evening and at the same time each day, on the day of injection and for 6 days following injection.

Participants' parent(s)/LAR(s) will record the following data in the eDiary:

- Solicited local and systemic reactogenicity ARs, as defined in [Section 7.4.3](#), that occur on the day of each vaccine administration and during the 7 days after vaccine administration (ie, the day of injection and 6 subsequent days). If a solicited local or systemic AR continues beyond Day 7 after vaccination, the participant's parent(s)/LAR(s) will be prompted to capture details of the solicited local or systemic AR in the eDiary until it resolves or the next IP injection occurs, whichever occurs first. Capture of details of ARs in the eDiary should not exceed 28 days after each vaccination. Adverse reactions recorded in the eDiary beyond Day 7 should be reviewed by the study site staff either during the next scheduled telephone call or at the next study site visit.
- Daily oral (for participants  $> 4$  years of age) or tympanic (for participants  $\leq 4$  years of age) body temperature measurement should be performed at approximately the same time each day using the thermometer provided by the study site. If body temperature is taken more than once in a given day, only the highest temperature reading should be recorded.
- Measurement, as applicable, for solicited local ARs (injection site erythema and swelling/induration); the size measurements will be performed using the ruler provided by the study site.
- Any medications taken to treat or prevent pain or fever on a day of injection or for the next 6 days.

The eDiary will be the only source document allowed for solicited systemic or local ARs (including body temperature measurements). Participants' parent(s)/LAR(s) will be instructed to complete eDiary entries daily. The participant's parent(s)/LAR(s) will have a limited window on the following day to complete assessments for the previous day; quantitative temperature recordings and measurement of any injection site erythema or swelling/induration reported on the following day may be excluded from the analyses of solicited ARs.

Any new safety information reported during safety telephone calls or at study site visits (including a solicited reaction) that is not already captured in the eDiary will be described in the source documents as a verbally reported event. An event reported in this manner must be described as a solicited event and entered on the solicited AR eCRF.

Study site staff will review eDiary data with participants' parent(s)/LAR(s) at telemedicine visits 7 days after each injection.

The eDiary will also be used every 4 weeks, starting at Day 71 through Day 183 and again starting at Day 223 through Day 363 for Parts 1 and 2 and starting Day 71 through Day 183 and again starting at Day 191 through Day 303 for Part 3, to capture the occurrence of AEs, MAAEs, SAEs, AESIs, or AEs leading to withdrawal.

As specified in the SoAs ([Section 10.1](#)), where applicable, the eDiary will prompt the participant's parent(s)/LAR(s) to complete an eDiary questionnaire that collects the following data:

- Changes in health since last completing the questionnaire or since in contact with the study site
- Any MAAEs, AESIs, or SAEs
- Known close contact with someone in the household who has known COVID-19 or SARS-CoV-2 infection. Per the CDC, "close contact" to someone with COVID-19 is defined as follows:
  - Being within 6 feet for a total of 15 minutes or more
  - Providing care at home
  - Having direct physical contact (hugged or kissed them)
  - Sharing eating or drinking utensils
  - Being sneezed or coughed upon or getting respiratory droplets on the participant
- Any experience of symptoms of COVID-19

If an eDiary record results in identification of relevant safety events according to the study period or of symptoms of COVID-19, a follow-up safety telephone call will be triggered.

Completion of eDiary questionnaires will alternate with safety telephone calls ([Section 7.1.2](#)) as the procedure for safety follow-up approximately every 4 weeks; these safety telephone calls will take place from Day 85 through Day 197 and again from Day 237 through Day 377 ([Table 12](#)). For Part 3, these safety telephone calls will take place from Day 85 through Day 197 and again from Day 205 through Day 317 ([Table 17](#)).

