### 3.1.1 Study Periods

This study involves up to 8 scheduled visits including up to 6 in-person visits (if screening and baseline are done separately) and 2 telemedicine visits (Visit 2 and Visit 4; remote visit by means of telecommunication technology). An additional in clinic visit (Visit 4S) will be conducted for a cohort of participants from selected Vaccine and Treatment Evaluation Units (VTEU) sites on Day 43 (2 weeks after Dose 2 of mRNA-1273 or placebo) for exploratory serology and cell-mediated immunity (CMI; S protein-specific T-cell responses) in Part 2 of the study.

If participants in Parts 1 and 2 decide to receive a booster dose, the booster study visit schedule ([Table 15](#)) and blood draw schedule ([Table 16](#)) will be utilized.

The study duration for each participant will vary depending on whether they choose to receive a booster or not; without a booster dose, it will be approximately 14 months, which includes 1 month for screening (Day -28 to Day -1), 1 month for dosing (on Day 1 and Day 29), and 12 months of follow-up after the second dose to monitor for safety, tolerability, reactogenicity, immunogenicity, and efficacy. With a booster given, the study duration will be up to 24 months.

For Study Arm 14, the study duration will be up to 17 months, which includes 1 month for screening (Day -28 to Day -1), at least 5 months for dosing (on Day 1, Day 29, and a third on Day 149/BD-Day 1), and 12 months for follow-up after the third dose of investigational product (IP).

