### **3.1.1.2 Treatment and Follow-up Period**

On Day 1, after the completion of the scheduled assessments ([Table 12](#) and [Table 17](#)), participants will be administered a single IM dose of the IP mRNA-1273 (25, 50, or 100  $\mu$ g) or placebo. Placebo will be administered only to those participating in Part 2 of the study. The procedures for IP administration will be detailed in the mRNA-1273-P204 Pharmacy Manual. Participants will be closely monitored for safety and will remain at the study site for observation

for at least 30 minutes after dosing. On Day 29, the second dose of IP will be administered. If the visit for the second dose (Day 29) is disrupted and cannot be completed at Day 29 (+7 days) as a result of the COVID-19 pandemic (self-quarantine or disruption of study site activities following business continuity plans and/or local government mandates for “stay at home” or “shelter in place”), the visit window may be extended to Day 29 + 21 days. When the extended visit window is used, the remaining study visits should be rescheduled to follow the intervisit interval from the actual date of the second dose. Participants will be monitored for 12 months after the second dose of IP (or booster) or 12 months after their third dose (Part 3) of IP, if applicable and whichever is longer for safety, immunogenicity assessments, and biomarker samples.

To test for the presence of SARS-CoV-2 by RT-PCR, nasal swab samples will be collected before the injections on Day 1, Day 29, Day 43 (if applicable per SoA), Day 57, Day 209, and Day 394. For Part 3, participants will have a nasal swab sample collected before the injections on Day 1, Day 29, Day 57, Day 149/BD-Day 1, Day 177/BD-Day 29, Day 329/BD-Day 181, and Day 514/BD-Day 366, according to the schedule of assessments (SoA; [Table 12](#) and [Table 17](#)). Participants who test positive at baseline may receive Dose 2 as long as they remain asymptomatic at the time of dosing.

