2. If the visit for the second dose (Day 29) is disrupted and cannot be completed at Day 29 (+7 days) as a result of the COVID-19 pandemic (self-quarantine or disruption of study site activities following business continuity plans and/or local government mandates for “stay at home” or “shelter in place”), the visit window may be extended to Day 29 + 21 days. When the extended visit window is used, the remaining study visits should be rescheduled to follow the intervisit interval from the actual date of the second dose. Refer to [Section 6.1.1](#) for individual participant criteria for delay of study vaccination.
3. To be conducted during Part 2 of the study in a cohort of participants at selected VTEU sites only.
4. All scheduled study visits should be completed within the respective visit windows. If the participant is not able to attend a study site visit as a result of the COVID-19 pandemic (self-quarantine or disruption of study site activities following business continuity plans and/or local government mandates for “stay at home” or “shelter in place”), a telemedicine visit should be conducted in place of the study site visit. The telemedicine visit should encompass all scheduled visit assessments that can be completed remotely, such as assessment for AEs and concomitant medications (eg, as defined in scheduled safety telephone calls). Home visits will be permitted for all nondosing visits, with the exception of Screening, if a participant cannot visit the study site as a result of the COVID-19 pandemic. Home visits must be permitted by the study site IRB and the participant’s parent(s)/LAR(s) via informed consent and have prior approval from the Sponsor (or its designee).
5. Safety follow-up via an eDiary questionnaire will be performed every 4 weeks from Day 71 to Day 183 and again from Day 223 to Day 363.
6. Safety follow-up via a safety telephone call will be performed every 4 weeks from Day 85 to Day 197 and again from Day 237 to Day 377.

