- 3. All scheduled study visits should be completed within the respective visit windows. If the participant is not able to attend a study site visit as a result of the COVID-19 pandemic (self-quarantine or disruption of study site activities following business continuity plans and/or local government mandates for “stay at home” or “shelter in place”), a telemedicine visit should be conducted in place of the study site visit. The telemedicine visit should encompass all scheduled visit assessments that can be completed remotely, such as assessment for AEs and concomitant medications (eg, as defined in scheduled safety telephone calls). Home visits will be permitted for all nondosing visits, with the exception of Screening, if a participant cannot visit the study site as a result of the COVID-19 pandemic. Home visits must be permitted by the study site IRB and the participant’s parent(s)/LAR(s) via informed consent and have prior approval from the Sponsor (or its designee).
- 4. Safety follow-up via an eDiary questionnaire will be performed every 4 weeks from Day 71 to Day 183 and again from Day 191 to Day 303.
- 5. Safety follow-up via a safety telephone call will be performed every 4 weeks from Day 85 to Day 197 and again from Day 205 to Day 317.
- 6. A full physical examination, including body temperature (oral [for participants > 4 years of age] or tympanic [for participants ≤ 4 years of age]), length/height, and weight, will be performed at the Screening Visit or on Day 1. Symptom-directed physical examination will be performed on Day 1, Day 29, Day 57, Day 149, Day 329, and Day 514 and may be performed at other time points at the discretion of the investigator. Body mass index will be calculated only at Screening Visit. Body temperature (oral/tympanic) should be measured on each injection day prior to injection. On each injection day before injection and again 7 days after injection, the injection site should be examined. Any clinically significant finding identified during a study visit should be reported as an MAAE. Participants who are febrile (body temperature ≥ 38.0°C/≥ 100.4°F) before injection on Day 1 Day 29, or Day 149 must have the visit rescheduled within the relevant visit window to receive the injection. Afebrile participants with minor illnesses may be injected at the discretion of the investigator.

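### Part 3 schedules no safety contact for 185 days, from the Day 329 visit to the Day 514 visit, although MAAEs, SAEs and AESIs are primary endpoints for the whole study

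*Protocol*

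**What the plan says.** Section 7.1.1 alternates eDiary questionnaires with safety calls "as the procedure for safety follow-up approximately every 4 weeks" and then gives the dates for each part. In Part 3 the questionnaire runs from Day 71 to Day 183, "again starting at Day 191 through Day 303 for Part 3, to capture the occurrence of AEs, MAAEs, SAEs, AESIs". The calls are set out as follows: "For Part 3, these safety telephone calls will take place from Day 85 through Day 197 and again from Day 205 through Day 317". Footnotes 4 and 5 to Table 17 repeat these dates; for the calls, "every 4 weeks from Day 85 to Day 197 and again from Day 205 to Day 317".

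Section 3.1.1.2 places the later Part 3 clinic visits, at which swabs are taken, on "Day 149/BD-Day 1, Day 177/BD-Day 29, Day 329/BD-Day 181, and Day 514/BD-Day 366". Table 17 has no column between the last two. Section 3.1.1 plans "12 months for follow-up after the third dose" of investigational product.

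Section 2 (Table 2) lists MAAEs, SAEs and AESIs over the whole study among the primary endpoints for the safety of the booster or third dose.

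Two other schedules cover a matching interval:
- Table 15 (mRNA-1273 booster, Parts 1 and 2) has a safety call at 270 days, between its 180-day and 365-day visits.
- Table 12 (two-dose schedule, Parts 1 and 2) has eDiary questionnaires from Day 223 to Day 363 and calls from Day 237 to Day 377, between the Day 209 and Day 394 visits.

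**The concern.** A primary safety endpoint that covers the whole study needs reasonably even ascertainment over that time. Section 7.4.7 ties the standard adverse event question to site visits and telephone contacts. Where none is scheduled, the site learns of an event only if the family volunteers it or comes in unprompted.

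Three things are at stake in the last half-year of Part 3:
- Milder medically attended events may be forgotten or misdated by Day 514.
- AESIs and SAEs must be reported within 24 hours of the site becoming aware of them, but that awareness may come months late. Review by the cardiac adjudication committee and the DSMB would then be late too.
- A family that drifts away after Day 329 may not be noticed until it misses Day 514, because Section 6.5 recognises loss to follow-up through failure to return for scheduled visits.

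**Working it through.** **Day mapping.** Study day = 149 + (BD-day − 1). BD-Day 181 gives 149 + 180 = 329, and BD-Day 366 gives 149 + 365 = 514. Both agree with the protocol.

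**Part 3 contacts after the third dose (Section 7.1.1, Table 17).**
- eDiary, second series, every 28 days: Days 191, 219, 247, 275, 303.
- Calls, second series, every 28 days: Days 205, 233, 261, 289, 317.
- Tail of the first series: eDiary Days 155 and 183; calls Days 169 and 197.
- Visits: Days 149, 156 (telemedicine), 177, 329, 514.

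**The gap.** 514 − 329 = 185 days. As a share of the year after the third dose, 185 / (514 − 149) = 185 / 365 = 50.7%. Both visits have ±14-day windows, so the range runs from (514 − 14) − (329 + 14) = 157 days to (514 + 14) − (329 − 14) = 213 days. Every other interval between consecutive scheduled Part 3 contacts is at most 21 days.

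**Same interval elsewhere.**

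| Schedule | Interval | Scheduled contacts inside it |
|---|---|---|
| Table 17, Part 3 third dose | Day 329 to 514 (185 days) | none |
| Table 15, mRNA-1273 booster | 180 to 365 days after dose (185 days) | one call at 270 days |
| Table 12, two doses | Day 209 to 394 (185 days) | 6 questionnaires and 6 calls; longest gap 394 − 377 = 17 days |

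**Could another mechanism fill the gap?** Section 7.3.2 describes COVID-19 symptom surveillance by telephone or eDiary. It applies only while some age group in Part 2 is blinded and is then discontinued, and Amendment 9 removed it from the schedule tables. It also works through the Section 7.1.1 contacts, which have ended by Day 317.

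**Effect of the change.** A call 270 days after the dose falls on Day 149 + 270 = 419 and splits the gap into 419 − 329 = 90 and 514 − 419 = 95 days. Continuing the questionnaire every 28 days gives Days 343, 371, 399, 427, 455 and 483. The longest remaining gap is then 514 − 483 = 31 days.

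**The case against.** Section 7.1.1, Table 17 and its footnotes agree with one another, so this is a choice about contact density and not a contradiction. Concentrating contacts in the first six months after an extra dose is also the protocol's pattern elsewhere. Table 15 places its regular follow-up block before the 180-day visit, and Table 19 (mRNA-1273.214) ends follow-up at BD-Day 181. All of that stands, and it limits what can be claimed.

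A reader might infer several stronger points that the documents do not support:
- **Twelve contacts against none.** That count comes from Table 12, which follows children after two doses. The nearer analogue is Table 15, where the contrast is one call against none.
- **Events in the gap go uncollected, or children lost after Day 329 contribute nothing.** Unscheduled visits are allowed at any time (Section 7), unsolicited complaints are a recognised source (Section 7.4.12), and Day 514 records MAAEs, SAEs and AESIs. Section 6.5 asks for repeated contact attempts before a child is declared lost. These routes are passive or late, but they exist.
- **The 25 µg regimen will look safer than the Part 2 regimen.** No formal safety comparison of Part 3 with Part 2 is planned. Safety summaries are descriptive (Section 8.5.2), and the Part 3 hypothesis tests are immunogenicity comparisons with Study P301 adults (Section 8.2).
- **Half of the study period is uncovered.** The 51% refers to the year after the third dose. Against 514 study days it is 185 / 514 = 36%.

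The objection does not supply a reason why Part 3 lacks even the single late call that Table 15 provides, and the protocol gives none.

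**Conclusion.** The gap is real: 185 nominal days (157 to 213 with the windows), 51% of the year after the third dose, in about 300 children, with no scheduled contact for endpoints the protocol calls primary. The likely consequences are longer recall (about 6 to 7 months at Day 514), later detection, and possible loss of information for children who miss that visit. Serious events are more likely to surface unprompted than minor medically attended ones.

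The size of any undercount cannot be derived from the document, and a bias between regimens should not be asserted. The calculation assumes nominal visit days with the third dose on Day 149, and counts only scheduled contacts. The point is a cheap improvement to follow-up, not an error that invalidates an analysis.

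**What to change.** In Section 7.1.1 and Table 17 (a new column between Day 329 and Day 514, with footnotes 4 and 5 updated):
- Add at least one safety call about 270 days after the third dose (about Day 419), as in Table 15.
- Preferably also continue the existing 4-weekly eDiary questionnaire from Day 329 to Day 514 (Days 343 to 483).
- Keep the contacts on Days 155, 169, 183 and 197. They look redundant beside the second series, but for a child dosed on Day 149 they fall in the early weeks after the dose. For a child dosed late or not at all, they are the scheduled follow-up. Moving them would trade early ascertainment for late.

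The cost is schedule wording, eDiary configuration, and one call or a few extra prompts for about 300 families. The eDiary and the call script are already in use, and no dosing or clinical management rule changes.

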### **Ancillary Supplies for Participant Use**

Study sites will distribute Sponsor-provided oral or tympanic thermometers and rulers for use by participants' parent(s)/LAR(s) in assessing body temperature and injection site reactions for

recording solicited ARs in electronic diaries (eDiary). Based on availability, smartphone devices may be provided to those participants' parent(s)/LAR(s) who do not have their own device to use for eDiary activities.

### **7.1.2 Safety Telephone Calls**

A safety telephone call is a telephone call made to the participants' parent(s)/LAR(s) by trained study site personnel. This call will follow a script, which will facilitate the collection of relevant safety information. Safety telephone calls follow a schedule for each participant as indicated in the SoAs ([Section 10.1](#)). The participants' parent(s)/LAR(s) will be interviewed according to the script about the occurrence of AEs, MAAEs, SAEs, AESI, AEs leading to study withdrawal, concomitant medications associated with those events, and any nonstudy vaccinations ([Section 7.4.7](#)). In addition, study personnel will collect information on known participant exposure to someone with known COVID-19 or SARS-CoV-2 infection and on participant experience of COVID-19 symptoms. All safety information collected from the telephone contact must be documented in source documents as described by the participant's parent(s)/LAR(s) and not documented on the script used for the safety telephone contact. As noted in [Section 7.1.1](#), an unscheduled follow-up safety telephone call may be triggered if an eDiary record results in identification of a relevant safety event.

### **7.1.3 Safety Laboratory Assessments**

No scheduled laboratory assessments for safety are planned. This is based on the absence of clinically significant abnormal laboratory findings in the Phase 1 and Phase 2 studies of mRNA-1273 in adults.

A point-of-care urine pregnancy test will be performed, if deemed appropriate by the investigator, at the Screening Visit and before each vaccine dose in female participants of childbearing potential. At any time during the study, a pregnancy test either via blood or point-of-care urine can be performed, at the discretion of the investigator.

Febrile participants at dosing visits (fever is defined as a body temperature  $\geq 38.0^{\circ}\text{C}/\geq 100.4^{\circ}\text{F}$ ) may have visits rescheduled within the relevant study visit windows. Afebrile participants with minor illnesses may receive the IP at the discretion of the investigator.

